#### **3.3 Exploratory Objectives**

- 1) To define radiomic signatures on multiparametric MRI that select regions of the prostate that are likely to harbor more aggressive disease.
- 2) To molecularly characterize tissue from the multiparametric habitat-directed prostate biopsies and develop genomic signatures of indolent versus progressing prostate cancer using a 1.4 million feature oligonucleotide microarray capable of global high throughput analysis of formalin fixed paraffin embedded specimens.
- 3) To relate radiomics and genomics signatures to existing urine, serum and tissue biomarkers that have been associated with prostate cancer diagnosis and/or progression.
- 4) To determine the incremental benefit of mpMRI, genomic risk testing, and molecular markers at baseline compared to NCCN risk class for predicting reclassification on confirmatory baseline biopsy.
- 5) To evaluate serial changes in mpMRI, genomic risk scores and molecular markers and relate them to progression on active surveillance.

### **4. STUDY DESIGN**

Single arm therapeutic trial investigating the impact of MRI and MRI-US fusion biopsy to identify higher grade or volume tumors early on for better selection of patients for active surveillance and improved outcomes for those undergoing delayed treatment after initial observation. MRI-US fusion biopsy will include targeting of suspicious areas seen on MRI as well as segmented sampling of the remaining gland. Patients will

undergo MRI and MRI-US fusion biopsy within 3 months of enrollment in the trial and have repeat MRI-US fusion biopsies every year to assess overall rates and the temporal distribution of progression. Serum, urine and prostate biopsy tissue will be serially collected to investigate the association between various molecular biomarkers and radiologic and histological progression.

Patients who are found to have cancer progression will undergo either radical prostatectomy or prostate dose escalated (EQD2>78Gy) image guided radiotherapy of the prostate. Although patients will be encouraged to seek treatment at the University of Miami to continue follow up on trial, we understand that patients may select to be treated elsewhere and this would not be considered a deviation from the protocol. Men undergoing surgery will have their pathology specimen compared to men in the University of Miami active surveillance database who had surgery after initial surveillance without MRI. After surgery men will be followed every 3-6 months (+/- 2 months) for the first year, every 6-12 months (+/- 3 months) in the second year, and annually (+/- 6 months) thereafter up to 5 years post surgery. Any adjustments to this schedule will be permitted under the discretion of the clinician. A PSA of 0.2 ng/ml with a repeat value showing the same or higher will be used to define biochemical recurrence post radical prostatectomy. For men undergoing radiation therapy, the method and dose of radiation that will be delivered will be left to the discretion of the treating physician. For men undergoing radiotherapy of the prostate, follow up serum PSA testing should occur every 6 months (+/- 3 months) for the first 3 years and then annually thereafter (+/- 6 months) for up to 5 years post treatment.

A PSA of 2 ng/ml above the nadir will be used to define biochemical failure post radiation. Rates of biochemical recurrence post surgery or radiation will be compared to historical data of men being treated after initial surveillance at the University of Miami. The choice to use androgen deprivation therapy will be left to the discretion of the treating physician. Follow up and treatment protocols have purposely been made broad to allow enrollment on other interventional trials for which a patient may be eligible. If the patient enters a radiation oncology clinical trials, then the timing of PSA and other labs will be timed in accordance with the radiation treatment protocol.

The flow chart shown in **Figure 1** illustrates the surveillance portion of the sequence that patients will go through if entered in the study. The post treatment flow chart for those who progress has purposely been left out to avoid prevention of patients enrolling on other intervention trials for which a patient may be eligible. Patients will be recruited for protocol participation from the pool of men seen for management of prostate cancer by physicians at the University of Miami. Those patients that sign an informed consent form for the study will be screened by the study investigators for fulfillment of eligibility criteria. Once the University of Miami Pathologic review is completed and all eligibility requirements are met, the patient will be registered in the study. Additionally, the patient will be asked to participate in the Urology Active Surveillance database for comparison with other active surveillance patients available in that database.

#### **4.1 Accrual goal**

The accrual goal for this study is 230 patients or approximately 46 patients per year for 5 years.

#### **4.2 Duration of Study Participation**

The research study will end at 36 months from the initial protocol biopsy.

Duration of study treatment will be a maximum of 60 months from enrollment and four biopsies for patients who do not progress. After the end of study, the patient will be followed, if consented, in the department of Urology active surveillance database as per their clinician's standard of care.

## **5. STUDY ENTRY AND ENROLLMENT AND WITHDRAWAL**

### **5.1 Study Entry**

Study entry, as used in this protocol, will be defined as a subject signing informed consent. Study enrollment, as used in this protocol, will be defined as the investigator's confirmation of the subject's eligibility by signing an eligibility checklist.

### **5.2 Enrollment Procedures**

As per UM/SCCC Clinical Research Services policy, eligibility must also be reviewed by a CRS director or designee. The investigator or study coordinator will provide the following to a CRS representative:

- 1) Completed and signed protocol-specific eligibility checklist;
- 2) All pages of the original signed informed consent forms (ICFs), including HIPAA Form B;
- 3) Relevant source documents such as: subject medical history and physical exam, admission or discharge notes, diagnostic reports, pathologic confirmation of diagnosis, and relevant subject-specific written communication.

### **5.3 Cancellation Guidelines**

The following are reasons for withdrawal of subjects from the study:

- a subject does not meet the eligibility criteria, (the subject will be considered a screen failure).
- a subject withdraws consent,
- a subject dies during protocol participation or
- a study investigator decides the subject should be withdrawn from the study (e.g. subject non-compliance)

Contact the CRS representative, or e-mail the information including the reasons for withdrawal as soon as possible, but no later than 48 hours after the event/decision.

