### **6.1 Inclusion (Eligibility) Criteria**

- 1) Biopsy confirmed adenocarcinoma of the prostate within 18 months prior to enrollment;
- 2) Pre-enrollment prostate biopsy must consist of at least 8 cores;
- 3) Biopsy reviewed by a University of Miami Pathologist;
- 4) Serum PSA  $\leq$ 20 ng/ml within 3 months of study enrollment;

- 5) Age  $\geq$ 35 and  $\leq$ 85 years;
- 6) Ability to understand and willingness to sign a written informed consent document;
- 7) Patients must agree to undergo serial multiparametric MRI and MRI-guided biopsy;
- 8) Patients must agree to fill out the longitudinal psychosocial questionnaires assessing health related quality of life.

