## **10. STATISTICAL CONSIDERATIONS**

This is a single-arm trial with the primary objective of determining the rate of progression over 2 years in men undergoing AS who are managed with multiparametric-

MRI and MRI-US fusion prostate biopsies, as compared to historical controls. The primary study endpoint is the 24-month cumulative progression rate based on biopsy criteria.

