## 10.1 Primary Study Endpoints

### 10.1.1 Progression

The main study endpoint will be the 24-month cumulative progression rate. In the context of this trial, progression refers to a repeat surveillance biopsy indicating any one of the following: (i) more than 4 positive cores involving any grade of cancer, (ii) three or more cores with Gleason 3+4 cancer, (iii) any single core with Gleason 4+3 cancer or higher, (iv) a Gleason 3+3 at diagnosis that is upgraded to Gleason 3+4 or (v) undergoing treatment, regardless of histological progression. Although many existing active surveillance protocols incorporate volume of cancer in their definition of progression, these are based on random biopsy of the prostate. Critical volumes of cancer based on targeted biopsy have not been defined and will be explored in this analysis.

- Progression rate will be estimated for each scheduled surveillance biopsy as the proportion of study patients without prior progression for whom the biopsy indicates progression.
- Cumulative progression rate will be estimated for each of the four planned biopsies as the proportion of patients with progression among those having had all planned biopsies to date, or a previous biopsy indicating progression.

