## 10.5 Statistical Analysis

Descriptive statistics will be done for patient demographics and baseline disease characteristics. Counts and percentages will be used to summarize the distribution of categorical variables while median, range, mean and standard deviation will be used for continuous variables. Baseline characteristics will include age, race/ethnicity, T-stage, Gleason score, PSA, PSAD and performance status. Continuous scores will be compared using ANOVA and linear regression controlling for common demographic and clinical variables.

For each scheduled surveillance biopsy session, we will tabulate patients and the following status categories: biopsy indicating progression, biopsy negative for progression, biopsy not performed for progression detected on earlier biopsy, biopsy not performed because patient refused, or biopsy not performed because patient dropped out of study.

Time to event endpoints such as progression and BCR will be analyzed by Kaplan-Meier (KM) or competing risk (CR) methods. Where the Kaplan Meier method is used, point estimates and two-sided 95% confidence intervals for rates will be reported for selected times using Greenwood's variance and the log-log transform method. Median survival time, if attained, will also be reported. We will report the progression rate and the cumulative progression rate for each surveillance biopsy. Taking the third scheduled biopsy at the end of 2 years as illustration, the progression rate at 24 months is the proportion of biopsied patients indicating progression among the total number of biopsied patients over the 24 month period. The 24-month cumulative progression rate is the primary endpoint, which will include those who complete the first three biopsies or have progression from the first or second biopsy. The primary endpoint, 24-month cumulative progression rate, will be estimated and reported with corresponding 95% confidence intervals. Groups will be compared by the log rank test. In addition, we will report and plot the cumulative progression rates in each arm for the four scheduled surveillance biopsies. It is expected that the early difference with historical values and those obtained with MRI-guided biopsies will not be sustained; that is, the 36-month cumulative progression rates will be approximately equal. Similar estimation of time-specific and cumulative rates will be done for Histological progression.

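### Withdrawal for undefined non-compliance, with no outcome collection afterwards and a completers-only denominator, loses primary outcomes and leaves who is counted open to result-aware discretion

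*Combined protocol and SAP*

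**What the plan says.** Section 5.3 gives four reasons for withdrawing a subject. The last is that "a study investigator decides the subject should be withdrawn from the study (e.g. subject non-compliance"). It sets no threshold for non-compliance and no rule for data collection afterwards. It asks only that the clinical research office be told, with reasons, within 48 hours.

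Section 6.1 requires agreement at entry to serial MRI and MRI-guided biopsy (item 7) and to the questionnaires (item 8: "Patients must agree to fill out the longitudinal psychosocial questionnaires").

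Section 10 opens: "This is a single-arm trial with the primary objective of determining the rate of progression over 2 years". Section 10.1.1 lists as one form of progression "undergoing treatment, regardless of histological progression". It then defines the cumulative rate as "the proportion of patients with progression among those having had all planned biopsies to date, or a previous biopsy indicating progression". Section 10.5 says that the primary endpoint "will include those who complete the first three biopsies or have progression from the first or second biopsy". The same section tabulates, at each session, men whose biopsy was refused separately from those with "biopsy not performed because patient dropped out of study". It plans no sensitivity analysis for either group.

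Sections 7.3 and 7.9 provide for contact and continued follow-up, but for men with protocol-defined progression. Sections 4 and 4.2 describe an optional Urology surveillance database, which is not tied to the primary endpoint.

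**The concern.** The withdrawal decision belongs to people who can know the man's results. Under 7.4 the study team reviews every MRI, and under 7.5 the physician managing the biopsy is a co-investigator. The result is judged against a fixed historical 12.5%, so no control arm would share a selection effect.

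Two things are at stake. First, a man withdrawn before 24 months may later be treated or biopsied. Criterion (v) makes treatment a primary event, but no written procedure would find it. Second, he leaves both numerator and denominator. If withdrawal, or the effort made to retain a man, depends on his MRI, PSA or earlier biopsies, the rate among the remaining men differs from the rate among those enrolled.

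**Working it through.** **Inputs.** From 10.4: 12.5% historical rate, 25% target rate, 150 men analysed, two-sided 5% binomial test, 97.3% power, 10% dropout, and about 55 men per year for three years (55 × 3 = 165). Section 4.1 gives a different accrual goal, 230. The documents give neither the number withdrawn under 5.3 nor how many of them would progress; both are assumed below.

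**The plan's own figure.** For an exact binomial test with at most 2.5% in the upper tail and n = 150, the rejection limit is 28 or more events. P(X ≥ 28 | 150, 0.125) = 1.9% and P(X ≥ 28 | 150, 0.25) = 97.3%. The stated power reproduces.

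**Effect of selective loss.** Let N men be enrolled with true rate p, and let w be withdrawn, a share f of whom are events. The rate among the men retained is

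q = (N·p − w·f) / (N − w).

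The chance of rejecting is then the upper binomial tail at n = N − w and rate q.

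With N = 165 and w = 15, n = 150 and the limit is 28:
- f = p: q = p, so there is no bias. False-positive rate 1.9%, power 97.3%.
- p = 12.5%, f = 0: q = 20.625/150 = 13.75%. False-positive rate 5.6% against 1.9%.
- p = 25%, f = 0.5: q = (41.25 − 7.5)/150 = 22.5%. Power 89.1% against 97.3%.

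With N = 165 and w = 5, n = 160 and the limit is 30:
- p = 12.5%, f = 0: q = 20.625/160 = 12.9%. False-positive rate 2.2% against 1.5% without selection.

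With the 230 goal and w = 23 (10%), n = 207 and the limit is 37:
- p = 12.5%, f = 0: q = 28.75/207 = 13.9%. False-positive rate 6.3% against 1.6%.

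**Direction of the bias.** Suppose 16 men (10% of 165, rounded down) are withdrawn and the 149 retained show 25%, that is 37.25 events. Following up all 16 gives these rates:
- 10% of the 16 treated: (37.25 + 1.6)/165 = 23.5%.
- 25% treated: (37.25 + 4)/165 = 25.0%.
- 50% treated: (37.25 + 8)/165 = 27.4%.

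The retained-men estimate of 25% is therefore too high, right, or too low according to who left.

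**A repair that would not work.** Adding back only the treated men admits events without non-events. At a true 12.5% in everyone, the 149 retained men contribute 18.625 events. Suppose the 2 events among the 16 withdrawn men (16 × 0.125) are found as treatments and only those 2 men are added. The rate is then 20.625/151 = 13.7%, and the exact false-positive rate is about 5.6%.

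**Which rule removes whom.** A man who skips a biopsy without earlier progression already fails the denominators in 10.1.1 and 10.5, withdrawn or not. Section 5.3 adds two losses. It leaves no route to his later outcome, so a better denominator could not be filled. It can also remove a man who was up to date with his biopsies.

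**The case against.** The strongest reply is that 5.3 is not the main source of the loss. The completers-only denominators drop the man who misses a biopsy whether or not anyone withdraws him, and a later negative biopsy does not restore him. Section 10.5 also separates refusal from dropout, so the plan expects some men to refuse a biopsy and stay on study. Both points stand. They are why the denominator has to change along with 5.3.

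Three stronger readings are tempting, and the documents do not support them:
- **That withdrawal ends follow-up.** A reader might infer this, but 5.3 does not say so, and consenting men may be followed in the Urology database. What the text shows is that no section ties any later information to the endpoint.
- **That a missed questionnaire leads to withdrawal.** Items 7 and 8 of 6.1 are agreements at entry, and no section equates one missed form with non-compliance. The undefined term permits that reading but does not require it.
- **That the primary rate is necessarily understated.** Lost treatment events pull the estimate down and lost non-events push it up. The arithmetic shows either sign, or none.

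It is also fair to say that 15 withdrawals is close to an upper bound, because the 10% dropout covers all causes. With 5 withdrawals the effect is small.

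**Conclusion.** The concern holds as a joint defect of 5.3, 10.1.1 and 10.5: an undefined and discretionary withdrawal reason, no outcome collection afterwards, and a denominator that excludes the men affected. Nothing in the plan limits or tests result-dependent selection.

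On 165 enrolled, the illustrated size runs from no effect to a false-positive rate of 5.6% instead of 1.9%, or power of 89.1% instead of 97.3%. With 5 withdrawals, none an event, the false-positive rate is 2.2% against 1.5%. These figures rest on assumed withdrawal numbers and event shares. They show what the rules allow, not what will happen. The change is worth making because it is cheap and because outcomes not collected cannot be recovered at analysis.

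**What to change.** **Section 5.3.** Remove non-compliance as a reason for withdrawal from the study. State that a man who declines an MRI, a biopsy or a questionnaire stops only that procedure. Unless he withdraws consent, he stays on study and is followed for treatment and biopsy results, including biopsies done elsewhere, to 36 months.

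**Sections 10.1.1 and 10.5.** Keep all such men, treated and untreated, in the analysis. One route is the Kaplan-Meier or competing-risk approach already named in 10.5, reported as 24-month cumulative incidence. The other is a sensitivity analysis on all enrolled men, with best- and worst-case bounds for those whose 24-month status is unknown. The bounds are useful in either case, because a man who is untreated and unbiopsied has unknown histology, and censoring him assumes that his leaving is unrelated to his risk. Do not add back only the treated men. Reword the denominator so that a man treated without a progression biopsy is clearly counted under criterion (v).

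**Cost.** Protocol wording, plus coordinator time for a record review or a call for about 16 men (10% of 165). No new study procedure is needed.

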## **6. PATIENT SELECTION/ELIGIBILITY CRITERIA**

Patients with low to low-intermediate risk prostate cancer are eligible for the study. Eligibility criteria for involvement in the study have been made broad enough to allow for most men who have relatively low volume Gleason score 6-7 disease to participate. Patients will be recruited from the pool of men seen for management of prostate cancer by physicians at the University of Miami.

### **6.1 Inclusion (Eligibility) Criteria**

- 1) Biopsy confirmed adenocarcinoma of the prostate within 18 months prior to enrollment;
- 2) Pre-enrollment prostate biopsy must consist of at least 8 cores;
- 3) Biopsy reviewed by a University of Miami Pathologist;
- 4) Serum PSA  $\leq$ 20 ng/ml within 3 months of study enrollment;

- 5) Age  $\geq$ 35 and  $\leq$ 85 years;
- 6) Ability to understand and willingness to sign a written informed consent document;
- 7) Patients must agree to undergo serial multiparametric MRI and MRI-guided biopsy;
- 8) Patients must agree to fill out the longitudinal psychosocial questionnaires assessing health related quality of life.

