Despite a worldwide acceptance of active surveillance in men with low risk tumors, nearly a third of men will progress to requiring treatment within the first three years. Most active surveillance protocols select patients with low volumes of low grade tumor seen on diagnostic biopsy. However, unlike other solid tumors where a lesion is visualized on imaging and a needle is inserted directly into it, most methods of visualizing the prostate cannot reliably identify lesions that are localized to the prostate. As a result, the current standard for diagnosis involves visualizing the prostate via transrectal ultrasound and performing segmented biopsies of the gland for cancer detection because the tumor(s) is not usually identified clearly. Given the heterogeneous nature of prostate cancer, where both indolent and aggressive tumors may be found in the same gland and some tumors are located in regions of the prostate (e.g., anteriorly) not thoroughly sampled, this "sampling" approach may miss the dominant or high grade tumors, which are likely to be the drivers of progression.

This is confirmed by a 20-30% chance of seeing a higher grade or volume of tumor when a second biopsy is performed. Furthermore, data from surgical patients suggest that 20-30% of patients who appear to be good candidates for surveillance may harbor high-risk features within their prostates suggesting that their biopsy may have underestimated the aggressiveness or volume of tumor present. This highlights the need for serial biopsy, but also suggests that those patients who are likely to progress early are not truly progressing, but more likely to harbor higher risk tumors that were missed on initial biopsies; a process referred to as "reclassification". Therefore, men choosing active surveillance must understand that the biopsy may not reflect the true biology of their disease, and there is some inherent risk involved that they may lose their opportunity for cure while their tumor is being monitored.

The primary goal of active surveillance is to monitor tumors that are deemed not to require immediate treatment with the goal of timely intervention at the point of tumor

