## 7.2 Evaluations During Intervention\*

- Multiparametric MRI obtained at the University of Miami (+/-) 3 months of enrollment and at 12, 24, and 36 months from initial protocol prostate biopsy.

- MRIus-guided biopsies will be obtained at 0 to 3 months from enrollment (“initial biopsy”) and at 12, 24 and 36 month from initial biopsy.
- History and physical at the discretion of the treating physician. Treating physician can be outside of UM..
- Serum PSA will be done preferably every 6 months or at least once a year up to 36 months from the initial biopsy. If the subject progress, PSA should be done every 6 months (+/- 3 months) or at the discretion of the clinician for the first 3 years and then annually thereafter (+/-6 months) for up to 5 years post treatment.
- If possible, plasma and/or serum (up to 5 tubes) for research purposes (biomarkers) may be obtained at 0 to 3 months from enrollment and at 12, 24, and 36 months from initial biopsy (optional - patient may refuse),
- If possible, post prostate-massage urine (approximately 50 mL) may be collected for research purposes at 0 to 3 months from enrollment and at 12, 24, and 36 months from initial biopsy (optional - patient may refuse). Urine research collection will not be done if research funds are not available.
- Quality of Life surveys obtained 0 to 3 months after enrollment and every 12 months from initial biopsy:
  - Expanded Prostate Cancer Index Composite Questionnaire (EPIC+SF12)
  - Memorial Anxiety Scale for Prostate Cancer patients (MAX-PC)
  - Optional - Food Frequency Questionnaire (FFQ) will be collected only atbaseline.

*\* Follow-up evaluations and visits may occur  $\pm$  1.5 months around each scheduled 6-month timepoint. For example, for the 6 month follow-up, the patient may be seen anytime between 4.5 and 7.5 months from the time of the first prostate biopsy. For the 12-month follow-up, the patient may be biopsied between 10.5 and 13.5 months from the time of the first prostate biopsy. Since the first biopsy may be from between 0-6 months from the day the patient is enrolled, each subsequent calendar event is timed in reference to the time of that first biopsy.*

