### **10.4 Sample size, accrual rate and study duration**

We plan to accrue approximately 55 patients per year for the first three years of the study; this assumes a 10% dropout rate. The power (97.3%), is based on 150 patients, using a two-sided binomial test at the 5% significance level to detect an increase in the 24-month cumulative progression rate from 12.5%, as expected for AS historically, to 25% for MRI-AS. Enrollment will occur during the first 3.25 years. Enrollment will be completed at < 3.33 years from the enrollment of the last patient.

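### The 24-month progression rate is clocked from the first protocol biopsy, up to 21 months after diagnosis, but is tested against a fixed 12.5% whose time origin is not stated

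*Combined protocol and SAP*

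**What the plan says.** Three provisions set the trial's clock.

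- **Entry.** Section 6.1, item 1, requires "Biopsy confirmed adenocarcinoma of the prostate within 18 months prior to enrollment". The study calendar in Appendix II labels this the diagnostic biopsy.
- **First protocol biopsy.** The main text of section 7.2 states that "MRIus-guided biopsies will be obtained at 0 to 3 months from enrollment". The footnote to the same section differs: "Since the first biopsy may be from between 0-6 months from the day the patient is enrolled".
- **Later biopsies.** The footnote continues that "each subsequent calendar event is timed in reference to the time of that first biopsy". The visit window is 1.5 months either side; at month 12, for example, "the patient may be biopsied between 10.5 and 13.5 months from the time of the first prostate biopsy".

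Section 10.5 reads the primary endpoint at the third protocol biopsy (months 0, 12 and 24) and counts progression found at the initial one. Section 10.1.1 defines histological events by fixed limits on positive cores and grade, and by an upgrade from Gleason 3+3 at diagnosis to 3+4. Treatment without histological progression also counts.

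Section 10 describes the aim as "determining the rate of progression over 2 years in men undergoing AS". Section 10.4 takes the null value as a "24-month cumulative progression rate from 12.5%, as expected for AS historically". It gives no source, time origin or biopsy schedule for that value. Section 10.5 does not list time since diagnosis among the baseline characteristics and plans no adjustment of the primary comparison for it.

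**The concern.** The label of 24 months describes time since the first protocol biopsy. The event looks back further: disease that was missed at diagnosis, or that developed between diagnosis and that biopsy, is counted if it shows at any of the first three protocol biopsies. If the 12.5% covers 24 months from diagnosis, the trial rate has had longer to build up than its comparator, and part of any excess would be credited to MRI.

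Timing matters more than usual because the hypothesis in section 2 is itself about timing: more progression found early and less found late. Section 10.5 expects the early difference to have gone by month 36. An offset of several months between the two clocks could imitate some of the effect sought, and a single-arm test against a fixed value cannot show that it has done so. The documents do suggest that progression accumulates. Section 1.1 says that "nearly a third of men will progress to requiring treatment within the first three years", and section 1.5.1 reports 26% biopsy progression at a mean follow-up of 2.9 years.

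**Working it through.** **Reproducing the plan's figure.** Inputs from section 10.4: n = 150, null 12.5%, alternative 25%, two-sided 5% binomial test. The exact upper cut-off is the smallest r with P(X ≥ r | 150, 0.125) ≤ 0.025. P(X ≥ 27) = 0.0325 and P(X ≥ 28) = 0.0193, so r = 28. Power = P(X ≥ 28 | 150, 0.25) = 0.973, which matches the stated 97.3%.

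**Time from diagnosis to the month-24 biopsy.**

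- Shortest: 0 + 0 + 24 = 24 months.
- Longest, main text: 18 + 3 + 24 = 45 months (gap 18 + 3 = 21).
- Longest, footnote: 18 + 6 + 24 = 48 months (gap 24).
- Adding the 1.5-month window: 46.5 or 49.5 months.

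**Effect on the test if the 12.5% runs from diagnosis.** The documents do not say that it does, so this is an assumption. Let d be the gap in months, taken as equal for every man, and f the share of the 24-month hazard that acts during the gap. The rate with no MRI effect is

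p(d, f) = 1 − 0.875^(1 + f·d/24).

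The test is still run at 28 of 150. With f = 1 (constant hazard):

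- d = 6: 1 − 0.875^1.25 = 15.4%
- d = 10.5: 1 − 0.875^1.4375 = 17.5%
- d = 21: 1 − 0.875^1.875 = 22.1%

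Smaller f allows for two facts: the trial takes no biopsies during the gap, and disease missed at diagnosis does not increase with waiting. Neither d nor f is given in the documents. The table shows the chance of 28 or more events in 150 with no MRI effect; the nominal value is 1.9%.

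| Gap d (months) | f = 0.10 | f = 0.25 | f = 0.50 | f = 1 |
|---|---|---|---|---|
| 6 | 2.5% | 3.7% | 6.5% | 15.7% |
| 10.5 | 3.1% | 5.7% | 12.9% | 38.2% |
| 21 | 4.7% | 12.9% | 38.2% | 87.1% |

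If gaps were instead spread evenly over 0 to 21 months with f = 1 (also assumed), the mean rate would be 17.4% and the chance about 38%.

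**If the historical clock starts at a first re-biopsy after a similar gap.** The rescaling does not apply, and the chance stays at 1.9%.

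**Effect on power of a higher null.** With a null of 17.5%, the exact cut-off for 150 men is 37, and power at a true 25% is P(X ≥ 37) = 57%.

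**The case against.** A reader might infer that the comparison is biased toward the hypothesis as a matter of fact. The documents do not support that, for four reasons.

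- **The origin of the 12.5% is unknown.** The direction of any bias depends on it. Several sections count by biopsy number: the schema, the primary objective in section 3.1, and the centre's own experience in section 1.5.1 (7%, 18% and 17% at the first, second and third re-biopsy). The figure 12.5% equals (7 + 18)/2, though the plan does not say it was obtained that way. Historical men also waited between diagnosis and first re-biopsy, so a gap in both cohorts is not in itself a mismatch.
- **Constant hazard is a strong assumption.** Histological events are seen only at biopsy, and section 1.1 argues that many early progressors had disease missed at the outset. Such disease does not grow with the gap, which is why the smaller values of f belong in the range. Nor does the curve fit the centre's cohort: it gives about 17.6% at 2.9 years, where 26% is reported.
- **Not everything since diagnosis can count.** Section 6.2 excludes men above the core or grade limits on the reviewed biopsy and men with earlier pelvic radiotherapy or prostate surgery for cancer. This would lower the trial rate. The screen is incomplete: a man upgraded before entry from 3+3 to 3+4 in one or two cores stays eligible, yet a repeat 3+4 finding would count as progression.
- **The 87% is an extreme.** It needs every man to be at the 21-month limit.

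These points remove any claim of established bias and any single estimate of its size. They do not close the gap, because the plan gives no means of showing that the two clocks agree. Indexing by biopsy number does not do so either, since sections 10 and 10.4 state the tested quantity in months.

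**Conclusion.** The point holds conditionally. It is established that the month-24 biopsy can fall 24 to 45 months after diagnosis (48 by the footnote), that upgrading is measured from diagnosis, and that the 12.5% has no stated origin. Whether this distorts the test is not established.

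If the 12.5% runs from diagnosis or the start of surveillance, the comparison may favour MRI, with a false-positive chance anywhere from about 2.5% to 87% according to the gap and the share of hazard acting in it. If the historical clock matches the trial's, there is no distortion, and the exclusions in section 6.2 push the other way. The upper limit on the gap also assumes that the biopsy in section 6.1 is the original diagnosis, as the calendar implies. The matter should be settled before the primary comparison is made, because the result cannot be interpreted without it.

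**What to change.** Leave eligibility unchanged and amend sections 10.4 and 10.5.

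1. State the source, time origin and biopsy schedule of the 12.5%. Derive the historical rate from the centre's surveillance database on the trial's clock: cumulative progression to 24 months after first re-biopsy, in men with a comparable diagnosis-to-first-re-biopsy interval. If the null changes, restate the power.
2. Add the interval from diagnosis to first protocol biopsy to the baseline variables, report the primary rate by it, and pre-specify a sensitivity analysis in men with a short interval, for example 6 months or less. That cut-off is a suggestion; the documents do not supply one.
3. Reconcile the 0–3 and 0–6 month statements in section 7.2.

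The dates are already needed for eligibility and scheduling, so no new data are required from trial patients. The costs are an extraction from the surveillance database (whose ability to supply an interval-matched rate the documents do not show), fewer men and a wider confidence interval in the restricted analysis, and possibly a less favourable stated power, such as the 57% shown above for a null of 17.5%.
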